9. PLANNED INCLUSION/EXCLUSION CRITERIA

We will adopt a pragmatic approach to recruitment, i.e. aim to include all patients undergoing temporal artery biopsy for suspected GCA. A lower age restriction of 18 will be applied although no age criteria is necessary for this disease type as we expect the majority of patients to be elderly. The clinicians will be using their judgment and clinical experience to determine whether or not to refer for biopsy. We will include patients with pre-existing polymyalgia rheumatica. Most patients will be treated with a standard dose of prednisolone, but some may be commenced on prednisolone plus another immunosuppressive agent. They will be included even though we suspect that the biopsy and scan results may be affected differently than when compared to steroids alone.

9.1 Inclusion criteria

For the cohort study

- (1) A clinical suspicion of new diagnosis of GCA e.g. patients with a new onset of headache, scalp tenderness, with or without elevated CRP or ESR, jaw or tongue claudication with or without visual loss.
- (2) The clinician decides that the patient requires an urgent temporal artery biopsy to determine whether or not the diagnosis is GCA.
- (3) The patient agrees and provides NHS consent to undergo a temporal artery biopsy as part of standard care.
- (4) Patients have been started on high dose glucocorticoids or will be started on high dose glucocorticoids.
- (5) Patients must be willing to attend for an ultrasound scan of their temporal and axillary arteries.
- (6) Participants must be willing to give informed written consent or willing to give permission for a nominated friend or relative to provide written informed assent if they are unable to do so because of physical disabilities e.g. sudden onset of blindness/vision loss which can be caused by GCA (this will be made clear in the ethics approval application).
- (7) Must be 18 years of age or over.

For the training cases

- (1) Patients attending hospital outpatient or in patient departments for assessment for any condition (apart from giant cell arteritis or polymyalgia rheumatica) or healthy staff volunteers.
- (2) Above the age of 50 years.
- (3) Willing to attend for an ultrasound scan of their temporal and axillary arteries.
- (4) Willing and able to give written informed consent.

9.2 Exclusion criteria

For the cohort study

- (1) Previous diagnosis of GCA.
- (2) Use of high dose glucocorticoid (>20mg prednisolone/day) for management of current suspected GCA for more than 7 days prior to the dates of the ultrasound and biopsy.
- (3) Long term (>1 month) high dose (>20mg per day at any time) steroids for conditions other than PMR, within three months prior to study entry.
- (4) Inability to give informed consent (either written consent or verbal assent from a relative or carer)
- (5) Inability to undergo an ultrasound scans of the temporal and axillary arteries.
- (6) Patients with a known cause of headache (not due to GCA), or any condition which would preclude the need for a temporal artery biopsy.
- (7) Patients who are unable to undergo an ultrasound scan and a temporal artery biopsy within 7 days of starting glucocorticoids.

For the training cases

- (1) Diagnosis of suspected GCA or a previous history of diagnosed or suspected GCA.
- (2) Inability to give written informed consent.
- (3) Inability to undergo an ultrasound scans of the temporal and axillary arteries

10. ETHICAL ARRANGEMENTS

All patients recruited to the study will be incident cases with most being referrals from primary to secondary care. This study will meet the NIHR criteria for portfolio research and will therefore involve a full IRAS application with the support of the Thames Valley CLRN. Approval to conduct the study will be sought from each local Trust via Site Specific Information (SSI) Forms.

Potential participants will be approached by a member of the research team, and will be provided with a Participant Invitation Study Letter and Participant/Patient Information Sheet (PIS) and given the opportunity to discuss the research project prior to obtaining informed consent or assent. Verbal consent will be obtained from all clinicians responsible for the care of the potential participant in the first instance prior to approaching their patient. We foresee that potential participants will be identified following referral from Primary Care for assessment by the on-call rheumatologist. We will fully inform the on-call rheumatologists about the study; we will establish weekly contact with them and provide them with a Participant/Patient Information Sheet (PIS) for them to give to all potential participants. The PIS will inform the potential participant that a member of the research team, mainly the research nurse, will contact them to discuss the study in more detail. The PIS will welcome the potential participant to contact the research team to inform them of their decision to participate or not. Due to the nature of the study which is as a result of the requirement to undertake the ultrasound scan prior to the biopsy (both being required within 7 days of the participant commencing glucocorticoid therapy). An example of the 7 day timeframe is given below:

Time and Date participant started glucocorticoid therapy (Day 0):	10.30am on Monday 7 th February 2011
7 days deadline (Day 7): Within these days, Visit 1, ultrasound and biopsy need to be completed before the date opposite.	10.30am on Monday 14 th February 2011

No study related activity will be performed prior to obtaining fully written informed consent or assent. The intervention is a non invasive procedure which does not pose any additional risks, discomfort or anxiety to the patient and every effort will be made to ensure the participants are not caused undue anxiety.

Consent will be obtained for the use of anonymised biopsy and scan images from this study as a teaching tool. The participants will also be asked to give consent for their information to be held by the research team indicating that they are willing to be approached for involvement in future ethically approved GCA research. Participants will also be asked to consent to the use of their data and tissue collected as part of this study for future GCA research through the creation of a Biobank which would utilize blood, DNA and biopsy samples (see Appendix I). The creation of this Biobank will conform to all the requirements in place through the Data Protection Act (DPA) and Human Tissue Act (HTA) including procedures for a Data Custodian who would be responsible for setting up procedures to enable access to this data. Any future research not specified within this application would involve a separate ethical and funding application. If patients need to attend for a separate visit we will pay their transport costs.

To consider the question of research equipoise, we surveyed the proposed study centres to discover if any are already using ultrasound as part of the standard diagnostic workup. In 2 centres, ultrasound scanning of temporal arteries is being used, but the centres involved have accepted the study requirements, so that investigators will not be made aware of the scan results for any individual patient

11. RISKS AND BENEFITS

The use of a cohort design that reflects current practice reduces additional study risks to participants. We have identified two risks:

- (1) The potential for introducing a delay in performing a temporal artery biopsy in the appropriate time frame of within 7 days of starting glucocorticoid therapy, thereby leading to an increase in the number of false negative biopsies. This might result in a higher level of uncertainty for the clinician who has to decide whether or not to continue long term high dose glucocorticoid therapy. We do not anticipate this to be a germane issue; if there is any delay in obtaining the scan, we would exclude the patient from the study. In fact we anticipate that for the purpose of the study, we will have to streamline the clinical service to improve the links between rheumatologists and the biopsy service to reduce delay in investigating suspected cases of GCA. Patients and physicians may feel less certain about the diagnosis, if based on ultrasound assessment alone. This is not a risk in the current study since all patients will have conventional investigations. For cases of diagnostic uncertainty, in whom the clinical suspicion for a new diagnosis of GCA is intermediate, the patients may need to undergo both the ultrasound scan and a biopsy in order to improve the diagnostic accuracy. The effect of ultrasound results instead of or as well as a biopsy will be tested in a non-real setting, but based on the real cases recruited from the study
- (2) The potential for glucocorticoid therapy to be withdrawn in a biopsy-negative participant but the hidden ultrasound indicates strong evidence of GCA. In all biopsy-negative patients we will check the scan; if it is positive we will highlight this to the clinician immediately after the patient has been evaluated at the 2 week visit (the point at which treatment may be significantly reduced if the biopsy is negative). The clinician can change the diagnosis and treatment, but the patient would continue in the study. Data will be analyzed on an intention to treat basis. The number of these events will be recorded by the study coordinator and reviewed by the data monitoring committee.

Participants will be fully informed of the risks of the study. The information will be included in the Participant/Patient Information Sheet (PIS) and will be reiterated during the consent process. Participants will be fully informed about the study prior to enrolment. We plan for a member of the research team, mainly the research nurse, to contact potential participants by telephone to discuss the study. This will only be done after liaising with the on-call rheumatologist and ensuring that a Participant Invitation Study Letter has been given to all potential participants. We plan for the member of the research team to contact the potential participant within 72 hours of them commencing glucocorticoid therapy. In case of an emergency, where potential participants are unable to give written consent (for example if they have suffered sudden visual loss as a result of the suspected GCA) we would seek fully written informed assent from a nominated relative or friend. Patients will receive medication as part of their standard care; the study itself does not involve any medication. Study documentation will be stored for at least 5 years.

A member of the research study team, mainly the research nurse, will also identify and approach potential participants during routine or emergency outpatient clinics. They would provide the potential participant with the Participant Invitation Study Letter and Participant/Patient Information Sheet (PIS) and will discuss the study in more detail and to ascertain whether the potential participants wishes to participate in the study or not. We will normally offer the potential participant 24 hours to consider the study. However, we would in certain circumstances, for example (i) in an emergency to minimise delay in normal care (i.e. performing the biopsy), (ii) where sites are able to provide a fast turnaround time for performing the biopsy, we will offer the opportunity for participants to provide fully written informed consent in less than 24 hours from receiving the information about the study. Time would be made available at clinic to discuss the study in more detail if the potential participant would like to. Arrangements will be made to book the ultrasound and biopsy as soon as possible (within 7 days of commencing glucocorticoid therapy). Written informed consent maybe obtained on the day of the ultrasound scan to minimize participant visits to the hospital. We will also have to take into account the short window period of 7 days following commencing of glucocorticoid therapy. If the participant wishes to attend the hospital at a different time/day to their arranged ultrasound scan to go through the consent process then this will be arranged and their travel costs will be reimbursed; if this falls outside the 7 day window period then the participant will be unable to participate in the study.

12. TABUL STUDY - PROPOSED SAMPLE SIZE

A sample of 402 patients provides 90% power at a 5% type I error rate to test the joint hypothesis that

- (i) ultrasound has greater sensitivity than biopsy (to detect an increase in sensitivity from 76% for biopsy (assuming a 0.24 false negative fraction based on 9-44% biopsy-negative GCA) to 87% sensitivity for ultrasound^[5]; and
- (ii) to detect specificity of ultrasound of no less than 0.83 based on an expected specificity of 0.96^[5]. This sample size will allow estimation of a one-sided rectangular confidence region for ultrasound false and true positive fractions, assuming 80% prevalence of GCA in patients having a biopsy for suspected GCA, with the sample size inflated ($\gamma=0.1$) due to uncertainty in the proportion of cases/controls in a cohort design^[16].

In order to allow for losses to follow-up we plan to recruit 430 participants to the study. We anticipate that most losses to follow-up will occur in recruited participants not having both ultrasound and biopsy at their appointed time within 7 days of starting steroids. Previous experience of observational studies in PMR^[17] suggest no further losses at the week 2 assessment and 4% at the 6 month assessment. However, the primary outcome (reference standard diagnosis) can be derived in participants who do not complete the 6 month assessment. These assumptions will be checked using early monitoring of recruitment and follow-up rates, with recruitment targets modified as necessary.

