12.1 Statistical analysis

The analyses will be performed in accordance with a detailed analysis plan developed during the study that meets the reporting requirements of the STARD statement^[18]. The primary analyses will estimate:

- (i) the sensitivity of an abnormal ultrasound test (compared with an abnormal biopsy test) for predicting the reference standard diagnosis of GCA; and

- (ii) the specificity of an abnormal ultrasound test predicting the reference standard diagnosis of GCA against the null hypothesis that specificity is <83%.

Uncertainty in sensitivity and specificity will be estimated using a joint rectangular 95% confidence interval. No interim analysis is planned. Analysis of inter- and intra-rater agreement of ultrasound interpretation and biopsy interpretation will be assessed using kappa coefficients^[19]. Data from the expert panel rating appropriateness of diagnostic and treatment strategies will use the standard RAND/UCLA approach for determining consensus^[14]. A detailed analysis plan will be prepared to specify all a priori analyses including sub-group analyses (e.g. patients with high or low risk, patients with or without PMR, patients with or without visual symptoms at presentation), analysis by specific components of ultrasound and biopsy results (e.g. positive or negative axillary artery scans) and assessment of positive and negative predictive values of tests.

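### The sensitivity hypothesis is a paired comparison with biopsy, but the inference named in sections 12 and 12.1 is a region for sensitivity and specificity that cannot by itself support it

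*Protocol*

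**What the plan says.** Protocol section 12 states the size and error rates: "A sample of 402 patients provides 90% power at a 5% type I error rate to test the joint hypothesis that" two limbs hold. Limb (i) is comparative: "ultrasound has greater sensitivity than biopsy". Its planning value for biopsy is worded as follows: "to detect an increase in sensitivity from 76% for biopsy (assuming a 0.24 false negative fraction based on 9-44% biopsy-negative GCA". The value planned for ultrasound is 87%. Limb (ii) concerns ultrasound alone: "to detect specificity of ultrasound of no less than 0.83 based on an expected specificity of 0.96". The section then names the inference that the size serves: "This sample size will allow estimation of a one-sided rectangular confidence region for ultrasound false and true positive fractions". Four in five of those biopsied are taken to be cases (prevalence 80%), and the size is inflated at gamma = 0.1 for the random split between cases and controls.

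Section 8 gives every participant ultrasound and then biopsy, so limb (i) is a within-patient comparison.

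Section 12.1 item (i) sets ultrasound sensitivity beside biopsy and gives no null value. Item (ii) sets ultrasound specificity against a null of 83%. On uncertainty it says: "Uncertainty in sensitivity and specificity will be estimated using a joint rectangular 95% confidence interval". Further detail is left to a separate analysis plan, which is not shown.

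**The concern.** A rectangle for ultrasound's true and false positive fractions has two coordinates, and neither involves biopsy. To say anything about limb (i), its sensitivity edge must be compared with a number for biopsy. Only two are available: the planning value of 76%, or the biopsy proportion observed in the same patients and treated as known. The first ignores that biopsy sensitivity in this cohort may differ from 76%. The second ignores its sampling error and its correlation with ultrasound.

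Section 12.1 does not close the gap. It mentions the comparison with biopsy, but its interval is for sensitivity and specificity, not for a difference between tests. Neither section gives an assumed discordance, on which the power of any paired comparison depends. The study is meant to inform whether ultrasound can replace biopsy, so the inference behind the superiority claim should be one that can deliver it.

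**Working it through.** **Inputs.** From section 12: N = 402, joint power 90%, joint type I error 5%, sensitivity 0.76 (biopsy) against 0.87 (ultrasound), specificity 0.83 (null) against 0.96, prevalence 80%, gamma 0.1. Cases: 0.8 × 402 = 321.6, about 322; controls about 80. For a one-sided joint 95% rectangle each limb has alpha\* = 1 − sqrt(0.95) = 0.0253 (z = 1.9545) and beta\* = 1 − sqrt(0.90) = 0.0513 (z = 1.632). The biopsy-negative range of 9–44% gives a biopsy sensitivity of 0.56 to 0.91. Discordance is not in the protocol and is varied below.

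**1. The plan's own figure.** One-sample formula per limb: n = [z_a sqrt(p0 q0) + z_b sqrt(p1 q1)]² / (p1 − p0)².
- Sensitivity limb: 158.2 cases.
- Specificity limb: 65.7 controls.
- Smallest N with at least a 90% chance of enough cases or controls: 208 and 377.

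This plain reading gives 377, about 6% below 402. Near variants come closer: 392 if gamma is split as 1 − sqrt(0.9), and 404 with 1 − sqrt(0.975) and 90% power per limb. A paired calculation under conditional independence gives 321.2 / 0.8 = 401.4, hence 402, without the gamma step. The text does not show which method was used.

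**2. If the ultrasound bound were compared with 76%.** With 322 cases the exact one-sided rule at 0.0253 claims superiority at 260 or more positives (260/322 = 80.7%). Chance of that claim when both tests have the same true sensitivity:

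| Common sensitivity | Superiority claimed |
|---|---|
| 76% | 2.5% |
| 78% | 13% |
| 80% | 40% |
| 82% | 75% |
| 87% | 99.9% |

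The error also runs the other way. With ultrasound at 76% and biopsy at 60%, a true 16-point gain is claimed in 2.5% of trials. A paired test under conditional independence has discordance 0.76 × 0.40 + 0.24 × 0.60 = 0.448. Its power is Phi[(0.16 sqrt(322) − 1.9545 sqrt(0.448)) / sqrt(0.448 − 0.16²)] = Phi(2.40) = 99%.

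**3. If it were compared with the observed biopsy proportion taken as known.** With equal sensitivities p and within-case correlation r, the difference has variance 2pq(1 − r)/n, but the bound allows only pq/n. The approximate error is therefore 1 − Phi[1.9545 / sqrt(2(1 − r))]. Results, with simulated values for a Wald bound (322 cases, p = 0.76) beside them:

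| r | Formula | Simulated |
|---|---|---|
| 0 | 8.3% | about 9% |
| 0.3 | 4.9% | 5.6% |
| 0.5 | 2.5% | 3.1% |
| 0.6 | 1.4% | 1.8% |

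A Wilson bound gives about 7–8% at r = 0.

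**4. A paired test at the stated size.** Let p01 be the proportion of cases that are biopsy-positive and ultrasound-negative; its feasible range is 0 to 0.13. Total discordance is psi = 2 p01 + 0.11. Cases needed: n = [1.9545 sqrt(psi) + 1.632 sqrt(psi − 0.11²)]² / 0.11². Joint power combines this limb with specificity at N = 402 and a random number of cases.

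| p01 | Cases needed | Sensitivity power, 322 cases | Joint power, N = 402 |
|---|---|---|---|
| 0 | 112 | >0.999 | 0.98 |
| 0.04 | 197 | 0.996 | 0.98 |
| 0.0988 (conditional independence: 0.13 × 0.76) | 322 | 0.949 | 0.93 |
| 0.13 | 388 | 0.905 | 0.89 |

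With an exact test for specificity, the conditional-independence figure is 0.92. If the region is read as two-sided, it is about 0.85.

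**The case against.** The strongest reply is that the protocol contains no faulty decision rule. The 76% appears only as a planning value. Section 12.1 item (i) compares ultrasound with the biopsy test and gives no constant, whereas item (ii) does write out a fixed null, so the authors state one where they intend one. The interval sentence in 12.1 is not restricted to ultrasound. The choice of McNemar test or paired interval can properly sit in the analysis plan. The error rates in steps 2 and 3 depend on rules nobody has adopted, and the inflation in step 3 disappears once the two tests correlate at about 0.5 to 0.6 within cases.

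Much of this stands. A reader might infer that the analysis fixes biopsy at 76%, or that superiority will not be validly tested at all; the documents support neither. Nor do the two sections contradict each other on sidedness: one says one-sided and the other is silent.

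What the reply does not answer is that the protocol is not merely silent. It names an inference and presents the sample size as serving it, and that inference leaves out one of the two tests being compared. An analysis plan that specified a paired test would be replacing that basis, not filling in its detail.

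**Conclusion.** The concern holds as a mismatch between hypothesis and stated inference. A region for ultrasound's own fractions, or an interval for sensitivity and specificity, cannot alone establish that ultrasound is more sensitive than biopsy in the same patients. The size of the harm is conditional: about 40% false claims at a common sensitivity of 80% if 76% were used as the comparator, and one-sided error from about 9% down to below 2.5% if the observed biopsy proportion were treated as known.

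A reader might also infer that 402 is too small. It is not shown to be. At the planning sensitivities, 80% prevalence and one-sided bounds, joint paired power is about 0.89 to 0.98 over all feasible discordance; it falls just short of 90% only near maximum discordance. Since both tests are planned for everyone, the right analysis remains available. This is a correction to make before the results are analysed, not a flaw that undermines the study.

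**What to change.** In sections 12 and 12.1:
- Test hypothesis (i) on the paired difference in sensitivity among reference-positive participants, by McNemar's test or a score interval for paired proportions, at one-sided 1 − sqrt(0.95) = 2.53%.
- Test hypothesis (ii) by the matching one-sided bound for ultrasound specificity against 83%, and form the joint region on the sensitivity difference and ultrasound specificity.
- State the same sidedness in both sections.
- Restate the power for this procedure with its discordance assumption, for example about 0.92–0.93 under conditional independence and 0.89–0.98 over the feasible range.

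The cost is wording and one restated power calculation. No extra patients or data are needed.
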